The combination of SBRT of liver lesions with immunotherapy has been less well studied. A small series of five patients with unresectable hepatocellular carcinoma who were treated with SBRT followed by anti-PD1 antibodies had 1-year LC and OS rates of 100%. One patient had grade \geq 3 toxicities (pneumonitis and skin reaction), but no radiation-induced liver toxicity was noted⁴³.

Given the findings that patients with ES-SCLC and liver involvement have a poor prognosis and a limited response to chemo-immunotherapy, we aim to augment the systemic anti-tumor immune response with RT targeted to liver metastases administered in addition to standard of care treatment. Preclinical data shows that radiation upregulates MHC class I expression, increases tumor antigen release, enhances CD8+ T cell infiltration, modulates the tumor immune microenvironment and upregulates PD-L1 expression, and that immunotherapy can synergize with RT to enhance tumor regression. Prior clinical studies also support a synergistic role for these treatment approaches. We hypothesize that combination RT with chemo-immunotherapy

will lead to improved local control and progression free survival in ES-SCLC patients with liver involvement, and provide key insights into the mechanisms of immune response/evasion.

Administration of radiation at the beginning of cycle 2 of chemoimmunotherapy will allow patients to receive the putative immunogenic benefit of radiation without compromising prompt initiation of standard of care chemotherapy with cycle 1 while awaiting radiation planning.

4 INVESTIGATIONAL AGENTS

4.1 Atezolizumab

Atezolizumab is a humanized immunoglobulin (Ig) G1 monoclonal antibody that targets PD-L1 and inhibits the interaction between PD-L1 and its receptors, PD-1 and B7-1 (also known as CD80), both of which function as inhibitory receptors expressed on T cells. Therapeutic blockade of PD-L1 binding by atezolizumab has been shown to enhance the magnitude and quality of tumor-specific T-cell responses, resulting in improved anti tumor activity (Fehrenbacher et al. 2016; Rosenberg et al. 2016)^{44,45}. Atezolizumab has minimal binding to Fc receptors, thus eliminating detectable Fc-effector function and clinically relevant associated antibody-mediated clearance of activated effector T cells.

Atezolizumab shows anti-tumor activity in both nonclinical models and cancer patients and is being investigated as a potential therapy in a wide variety of malignancies. Atezolizumab is being studied as a single agent in the advanced cancer and adjuvant therapy settings, as well as in combination with chemotherapy, targeted therapy, and cancer immunotherapy. Atezolizumab is approved for the treatment of urothelial carcinoma, NSCLC, SCLC, and triple-negative breast cancer.

Refer to the Atezolizumab Investigator's Brochure for details on nonclinical and clinical studies.

4.1.1 Preclinical Data

Comprehensive pharmacology, PK, and toxicology evaluations have been undertaken with atezolizumab.

Atezolizumab binds to its target with high affinity and blocks binding to receptors B7-1 and PD-1. It was engineered to reduce its binding to Fc_Y receptors and exhibits minimal binding to human Fc_Y receptors. Several studies demonstrated enhanced anti-tumor immunity when administered to mice with established tumors of colorectal and melanoma origin, suggesting PD-L1 blockade as a compelling strategy for enhancing the anti-tumor T cell response in solid tumors.

The safety, pharmacokinetics, and toxicokinetics of atezolizumab were investigated in mice and cynomolgus monkeys to support intravenous (IV) administration and to aid in projecting the appropriate starting dose in humans. Given the similar binding of atezolizumab for cynomolgus monkey and human PD-L1, the cynomolgus monkey was selected as the primary and relevant nonclinical model for understanding toxicity and pharmacokinetics.

Overall, the nonclinical pharmacokinetics and toxicokinetics observed for atezolizumab supported entry into clinical studies, including providing adequate safety factors for the proposed Phase I starting doses. The results of the toxicology program were consistent with the

anticipated pharmacologic activity of down-modulating the PD-L1/PD-1 pathway and supported entry into clinical trials in patients.

For further details please refer to the IB for atezolizumab.

4.1.2 Clinical Pharmacokinetics and Immunogenicity

The clinical pharmacokinetics for atezolizumab have been derived from the following atezolizumab monotherapy studies: PCD4989g, JO28944, IMvigor210, IMvigor211, BIRCH, POPLAR, FIR, and OAK.

Per the IB, the pharmacokinetics of atezolizumab monotherapy have been characterized in patients in Study PCD4989g at doses 0.01 mg/kg to 20 mg/kg q3w, including the fixed dose 1200 mg (equivalent to 15 mg/kg). Exposure to atezolizumab increased dose proportionally over the dose range of 1 mg/kg to 20 mg/kg. While a subset of antidrug antibody (ADA)-positive patients in Study PCD4989g receiving 0.3 to 3 mg/kg atezolizumab q3w experienced a reduction of atezolizumab C_{min} to below the PK assay lower limit of quantification (LOQ), patients receiving 10 to 20 mg/kg atezolizumab, including the fixed 1200 mg dose, maintained geometric mean C_{min} that was in excess of both the LOQ and the target serum concentration of 6 µg/mL⁴⁶.

Based on an analysis of exposure, safety, and efficacy data, the following factors had no clinically relevant effect: age (21- 89 years), body weight, sex, albumin levels, tumor burden, region or race, renal impairment, mild hepatic impairment, level of PD-L1 expression, or ECOG status. Positive ADA status against atezolizumab led to approximately 13% reduction in overall exposure.

Combined atezolizumab PK data obtained in metastatic urothelial carcinoma patients from IMvigor210 and IMvigor211 and in NSCLC patients from BIRCH, POPLAR, FIR, and OAK were consistent with the Phase Ia Study PCD4989g popPK model estimates. These results suggest that atezolizumab PK characteristics are similar across a range of tumor types and studies.

Antidrug antibodies to atezolizumab have been observed at all dosing levels (\leq 1 mg/kg to 20 mg/kg and 1200 m). Treatment-emergent ADAs were detected at 1 or more post dose timepoints in ADA positive patients across 20 studies of atezolizumab used as monotherapy or in combination. ADA status appeared to have no clinically relevant impact on pharmacokinetics or safety. Although some variability was observed across the studies, overall, ADA status appeared to have no clinically relevant impact on efficacy.

The fixed dose of 1200 mg (equivalent to an average body weight-based dose of 15 mg/kg) administered every 3 weeks was selected on the basis of both nonclinical studies and available clinical data from PCD4989g; this was the dose used in the Impower133 study establishing the survival benefit of atezolizumab in combination with standard of care chemotherapy in ES-SCLC.

Please refer to the IB for additional data regarding clinical pharmacokinetics and immunogenicity.

4.1.3 Clinical Data to Date

As of May 2019, 101 Sponsor studies are ongoing with atezolizumab as a single agent or in combination with other therapies. Of these, efficacy or and/or safety data that are considered sufficiently robust and clinically relevant are available for more than 30 studies. The most efficacy data is available in NSCLC patients (n=1636) with trials including BIRCH, POPLAR, OAK, IMpower150, IMpower131, FIR and the NSCLC cohort of PCD4989g. Additionally 983 patients with metastatic urothelial carcinoma have been administered atezolizumab through PCD4989g, IMvigor210 and IMvigor211.

In NSCLC, use of single agent atezolizumab in the second and third line setting in the PCD4989g, FIR, OAK, POPLAR and BIRCH trials resulted in a meaningful improvement in overall survival compared to standard of care across all PD-L1 expression groups. Additionally, IMpower132 demonstrated benefit of atezolizumab with chemotherapy in NSCLC.

The clinical data for atezolizumab in SCLC comes from the IMpower133. As found in the atezolizumab IB, IMpower133 was a Phase I/III randomized, double-blind placebo-controlled study of carboplatin and etoposide (CE) with or without atezolizumab (1200 mg) in patients with chemotherapy-naïve extensive-stage SCLC.

The study met the co-primary endpoints of OS and investigator-assessed PFS in the ITT population (n=403). As of the CCOD of 24 April 2018, 238 death events had been observed in the ITT population. A statistically significant and clinically meaningful improvement was demonstrated in OS with Atezo + CE (n=201) compared with placebo(PBO) + CE (n=202):stratified HR 0.701 (95% CI 0.541, 0.909; log rank p-value <0.0069; median OS 12.3 months vs. 10.3 months). A statistically significant improvement was also demonstrated in investigator-assessed PFS (stratified HR 0.772; 95% CI: 0.624, 0.955; log-rank p-value 0.017). Consistent with the benefit observed in the overall ITT population, an OS and PFS benefit with atezolizumab + CE arm compared with PBO + CE arm was observed in the majority of the subgroups analyzed. The ORR and median DOR were similar between the treatment arms. More patients in the atezolizumab + CE arm compared with the placebo + CE arm had an ongoing response at the time of the CCOD.

4.1.4 Safety Data to Date

From the IB, pooled safety data for atezolizumab monotherapy are available for 3178 treated patients in 8 studies: IMvigor210, IMvigor211, OAK, BIRCH, POPLAR, FIR, IMmotion150, and PCD4989g.

The majority of patients (over 97%) received atezolizumab at a dose of 1200 mg q3w, and the remaining patients, from Study PCD4989g, received atezolizumab at doses in the range of 1-20 mg/kg q3w. The safety data indicate that atezolizumab was well tolerated and the observed AEs were consistent with the known mechanism of action of atezolizumab or the underlying

Columbia University Irving Medical Center
Herbert Irving Comprehensive Cancer Center
CUMC IRB – AAAT0174

disease. The safety profile was generally consistent between the UC population (983 patients) and NSCLC population (1636 patients).

The majority (96.0%) of patients in the overall pooled population experienced at least one AE during the course of study treatment. Treatment-related AEs were reported in 68.2% of patients, with the most common events ($\geq 20\%$) being fatigue, decreased appetite, nausea, cough, constipation, dyspnea, and pyrexia.

In the pooled population of patients receiving atezolizumab monotherapy, Grade 3-4 AEs were reported by 46.5% of patients. The most common ($> 3\%$ of patients) events were anemia (5.0%), dyspnea (3.7%), fatigue (3.4%), hyponatremia (3.1%), and pneumonia (3.0%).

The overall incidence of Grade 5 AEs occurring within 30 days of last study drug intake or prior to initiation of non-protocol therapy was 3.8% (122/3178). Grade 5 AEs were reported in a variety of System Organ Classes (SOCs), and the following events were reported for more than 1 patient: death (19), pneumonia (12), sepsis (8), septic shock (5), respiratory failure (5), cardiac failure (3), sudden death (3), disease progression (3), myocardial infarction (2), lung infection (2), pulmonary sepsis (2), respiratory distress (2), pneumonia aspiration (2), pulmonary embolism (2), cerebral hemorrhage (2), cerebrovascular accident (2), ischemic stroke (2), embolism (2), and hepatic failure (2). Eleven Grade 5 events were considered by the investigator as treatment related; one case each of pulmonary hypertension, respiratory failure, death, intestinal perforation, pneumonia, sepsis, general physical condition abnormal, hepatic failure, cardiac failure, pericarditis constrictive, and toxic epidermal necrolysis.

The incidence of serious adverse events (SAEs) in the pooled population of patients receiving atezolizumab monotherapy was 41.2%. The most common SAEs were pneumonia (3.1%), dyspnea (2.8%), pyrexia (2.5%), UTI (1.9%) and pleural effusion, pulmonary embolism, and sepsis (1.3%).

Safety data is also available for atezolizumab in combination with chemotherapy, as proposed in this trial. In IMpower133 patients with ES-SCLC received atezolizumab 1200 mg IV on day 1, carboplatin at AUC 5 mg/ml/min on day 1 and etoposide 100 mg/m² IV on days 1-3 in 21 days cycles. In the combination atezolizumab+chemotherapy group, 94.9% of patients experienced a treatment related AE. 67.7% of patients experienced a grade 3-4 AE, compared to 63.3% with chemotherapy alone. The most common grade 3-4 AEs included neutropenia (22.7%), anemia (14.1%), and thrombocytopenia (10.1%) with combination therapy. Most immune related AEs (irAEs) were graded as 1-2, including rash (18.2%), hypothyroidism (12.6%), and hepatitis (6.1%) although grade 3-4 irAE also occurred including rash (2%), infusion-related reaction (2%), and hepatitis (1.5%). 3 patients in the atezolizumab+chemotherapy group experienced a death related to trial regimen including 1 from neutropenia, 1 from pneumonia, and one from an unspecified cause. 3 patients also died in the chemotherapy alone group (1 from pneumonia, 1 from septic shock, and 1 from cardiopulmonary failure).

4.2 Other Agent(s)

A platinum chemotherapy plus etoposide was the previous standard of care treatment for patients with ES-SCLC, and is still an approved regimen per the National Cancer Comprehensive Network guidelines. Carboplatin is preferred over cisplatin given equivalent efficacy with less risk of nephrotoxicity, neuropathy and otoxicity. The carboplatin-etoposide combination has been evaluated in several clinical trials⁴⁷⁻⁵⁰. The preferred dosing is etoposide 100 mg/m² on days 1, 2, and 3 and carboplatin AUC 5 on day 1 every 21 days. Toxicities associated with this regimen include grade 3/4 myelosuppression and infection. A meta-analysis of carboplatin based regimens in ES-SCLC reported a median OS of 9.4 months, PS of 5.3 months and an objective response rate of 66%¹³.

4.3 Radiation

[figure not shown]
Details regarding radiation administration can be found in Section 8.2.

5 STUDY DESIGN

5.1 General Design

This is a single-arm, open-label phase II study to assess the efficacy of liver-directed SBRT added to first-line atezolizumab, carboplatin, and etoposide in ES-SCLC, as measured by 6-month PFS. We hypothesize that the addition of SBRT, directed at liver metastases, to standard of care treatment atezolizumab+chemotherapy in SCLC patients will increase the 6-month PFS by 25% as compared to 20% historical control rate¹. A single stage design based on one-side exact binomial test will be used, with a type I error of 0.10 and a power of 80%. This design requires a total of 16 evaluable patients. If at least 6 out of 16 patients have not experienced progression at 6 months, this combination therapy will be considered worthy of further study. **Figure 1** depicts the study design. Schedules of assessments are provided in Study Calendar in **Section 12**.

Figure 1.

5.2 Intervention

All patients must undergo a mandatory biopsy of a liver lesion prior to chemotherapy initiation. Cycle 1 of chemoimmunotherapy will be administered as per standard of care, with radiation planning to be done subsequently in anticipation of liver-directed SBRT (3 doses of 10 Gy administered on alternating days to up to three liver lesions, measuring no greater than 5 cm each) to be given within +/-3 days of cycle 2.

Subjects will continue to receive study treatment (four 21-day cycles of induction chemoimmunotherapy followed by maintenance atezolizumab every 3 weeks) until disease progression or intolerance of treatment. During the maintenance phase, prophylactic cranial irradiation is permitted; consolidative thoracic radiation may be considered if deemed clinically appropriate by the treating investigator in discussion with the principal investigator.

If clinically feasible, it is recommended that the patient undergo a tumor biopsy sample collection at the time of radiographic disease progression. These data will be used to explore whether radiographic findings are consistent with the presence of a tumor. Additionally, these data will be analyzed to evaluate the association between changes in tumor tissue and clinical outcome and to further understand the potential mechanisms of progression and resistance to study treatment. This exploratory biomarker evaluation will not be used for any treatment-related decisions.

Patients will undergo tumor assessments prior to radiation administration and every 6 weeks (\pm 7 days) for the first 12 months following Cycle 1, Day 1, regardless of treatment dose delays. After 12 months, tumor assessments will be required every 9 weeks (\pm 7 days). Patients will undergo tumor assessments until radiographic disease progression per RECIST v1.1, withdrawal of consent, study termination by the principal investigator, or death, whichever occurs first.

Patients who continue treatment beyond radiographic disease progression per RECIST v1.1 will continue to undergo tumor assessments every 6 weeks (\pm 7 days), or sooner if symptomatic deterioration occurs. For these patients, tumor assessments should continue every 6 weeks (\pm 7 days), regardless of time in the study, until study treatment is discontinued.

Patients who discontinue treatment for reasons other than radiographic disease progression (e.g., toxicity) will continue scheduled tumor assessments at the same frequency as would have been followed if the patient had remained on study treatment (i.e., every 6 weeks [\pm 7 days] for the first 12 months following Cycle 1, Day 1 and then every 9 weeks [\pm 7 days] thereafter, regardless of treatment dose delays) until radiographic disease progression per RECIST v1.1, withdrawal of consent, study termination by the principal investigator, or death, whichever occurs first, regardless of whether patients start a new anti-cancer therapy.

5.3 Specimen Collection and Processing

Tumor Tissue

Tissue obtained from the pre-treatment liver biopsy will be processed for standard pathology evaluation and remaining tumor tissue will be partitioned and processed in the following ways:

- Snap-frozen in liquid nitrogen at -80 degrees Celcius for future DNA and RNA extraction

**Columbia University Irving Medical Center
Herbert Irving Comprehensive Cancer Center
CUMC IRB – AAAT0174**

- Processed as single-cell suspensions of tumor and infiltrating immune cells and then frozen at -80 degrees Celcius for future T-cell assays
- Processed as formalin-fixed tissue and embedded in paraffin for future IHC assays

Sufficient material must be collected to permit all planned correlative studies including (1) frozen material for DNA/RNA extraction, (2) FFPE material for IHC, and (3) digested cellular material for single-cell suspensions. Adjudication of sufficient material for (1) and (2) will be further certified by review of Diff-Quik or H&E stained slide/touch prep from frozen and FFPE material to ensure tumor is present in collected material. Adequacy of material for single-cell suspensions will be determined by collection of at least 20 million live cells total.

Peripheral Blood

- Mononuclear cells will be isolated from patients by centrifugation and cryopreserved for later analysis by ELISpot assay, FLOW cytometry, and/or CyTOF/CyTEK.
- Plasma will be stored for germline sequencing as a companion to somatic tumor DNA sequencing

Please see **Laboratory Manual** for further details.

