6.1 Inclusion Criteria

1. Age \geq 18 years
2. Histologically or cytologically confirmed ES-SCLC (per the Veterans Administration Lung Study Group [VALG] staging system)
3. No prior treatment for ES-SCLC
4. ECOG performance status 0 or 1
5. Patients with a history of treated, asymptomatic CNS metastases are eligible providing they meet the following criteria
 - Only supratentorial and cerebellar metastases allowed (i.e., no metastases to midbrain, pons, medulla or spinal cord)
 - No ongoing requirement for corticosteroids as therapy for CNS disease
 - No stereotactic brain radiation within 7 days
 - No evidence of interim progression between the completion of CNS-directed therapy and the screening radiographic study
 - Patients with new asymptomatic CNS metastases detected at the screening scan must receive radiation therapy and/or surgery for CNS metastases. Following treatment, these patients may then be eligible without the need for an additional brain scan prior to randomization, if all other criteria are met.

**Columbia University Irving Medical Center
Herbert Irving Comprehensive Cancer Center
CUMC IRB – AAAT0174**

6. At least one liver metastasis measuring 1 cm.
7. Measurable disease, as defined by RECIST v1.1, in addition to the liver lesion(s) to which SBRT is planned.
8. Patients must submit a pre-treatment tumor tissue sample from a liver metastasis. Tumor tissue must be obtained prior to the start of treatment.
9. Adequate hematologic and end organ function, defined by the following laboratory results:
 - ANC \geq 1500 cells/ μ L without granulocyte colony-stimulating factor support
 - Lymphocyte count \geq 500/ μ L
 - Platelet count \geq 100,000/ μ L without transfusion
 - Hemoglobin \geq 9.0 g/dL Patients may be transfused to meet this criterion.
 - INR or aPTT \leq 1.5 \times upper limit of normal (ULN)
This applies only to patients who are not receiving therapeutic anticoagulation; patients receiving therapeutic anticoagulation should be on a stable dose.
 - AST, ALT, and alkaline phosphatase \leq 5 \times ULN
 - *Serum albumin* \geq 25 g/L (2.5 g/dL)
 - Serum bilirubin \leq 1.25 \times ULN
 - Patients with known Gilbert disease who have serum bilirubin level \leq 3 \times ULN may be enrolled.
 - Serum creatinine \leq 1.5 \times ULN
10. For women of childbearing potential: agreement to remain abstinent (refrain from heterosexual intercourse) or use contraceptive methods as defined below:

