14. Serum chemistries include Albumin, alkaline phosphatase, total bilirubin, bicarbonate, BUN, calcium, chloride, creatinine, glucose, LDH, phosphorus, potassium, total protein, SGOT [AST], SGPT [ALT], sodium, and magnesium.
15. Thyroid function testing (TSH, free T3, free T4) collected at Cycle 1, Day 1 and every fourth cycle thereafter.
16. Serum pregnancy test must be performed within 14 days prior to C1D1.
17. HBV DNA must be collected on or before Cycle 1, Day 1 in patients who have negative serology for hepatitis B surface antigen and positive serology for HBcAb. HCV RNA must be collected on

**Columbia University Irving Medical Center
Herbert Irving Comprehensive Cancer Center
CUMC IRB – AAAT0174**

or before Cycle 1, Day 1 in patients who test positive for anti-HCV. Screening EBV serology samples will be collected, but tests will be performed only if patients subsequently experience an acute inflammatory event such as systemic inflammatory response syndrome while receiving study treatment.

18. Research Blood Samples are not to be collected on days when treatment is being delayed or held.
19. At screening, research bloods will be drawn for a) germline sequencing as a companion to somatic tumor DNA sequencing , b) T-cell subsets, and c) HLA-typing (see **Laboratory Manual**)
20. PBMC isolation, serum and plasma (see **Laboratory Manual**)

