13.8 Exploratory Biomarkers

An exploratory objective of this study is to identify potential biomarkers of response to the study treatment. Such blood and tissue biomarkers may provide evidence for the synergistic benefit of radiation with chemoimmunotherapy and may inform selection of patients most likely to benefit from this treatment. Biomarker analysis may include PBMC and tumor analyses including but not limited to TCR sequencing, flow cytometry, CITE-SEQ and CyTOF. Tumor specific analyses may

include, but not be limited to, whole exome and RNA sequencing, TCR sequencing, multiplex immunofluorescence analyses.

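### Section 5.3 names plasma, a cell-free fraction that can carry tumor DNA, as the germline comparator for tumor sequencing (minor; cheap improvement)

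*Combined protocol and SAP*

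**What the plan says.** The peripheral blood part of Section 5.3 has two bullets. One covers cells: "Mononuclear cells will be isolated from patients by centrifugation and cryopreserved for later analysis by ELISpot assay, FLOW cytometry, and/or CyTOF/CyTEK". The other covers the matched normal: "Plasma will be stored for germline sequencing as a companion to somatic tumor DNA sequencing". So plasma is assigned to the germline sequence and the cells are assigned to immune assays only.

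Section 12 (Study Calendar) adds two notes on research bloods. Note 19 reads "At screening, research bloods will be drawn for a) germline sequencing as a companion to somatic tumor DNA sequencing" and goes on to T-cell subsets and HLA-typing. It does not say which fraction supplies the germline DNA. Note 20 lists "PBMC isolation, serum and plasma". The calendar row carries both notes at screening and note 20 alone at later visits. Section 5.3 and both notes refer to a Laboratory Manual that is not among the documents.

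Section 13.8 gives the use: "An exploratory objective of this study is to identify potential biomarkers of response to the study treatment". Among the tumor analyses it lists as possible are "whole exome and RNA sequencing, TCR sequencing, multiplex immunofluorescence analyses".

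On the state of disease at the draw, Section 6.1 requires "No prior treatment for ES-SCLC", at least one liver metastasis, and measurable disease beyond the liver lesions planned for SBRT.

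**The concern.** A matched normal tells inherited variants from tumor variants, so it should be free of tumor DNA. Plasma DNA is cell-free and is shed by many tissues, tumor among them. The draw at screening comes before any treatment, with metastatic disease in place. If the comparator contains tumor DNA, a mutation that is truly somatic can also appear there and be discarded as germline.

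What is at stake is the quality of somatic calls in the exploratory work. The loss rises with the tumor fraction in plasma, so it can differ from patient to patient. In a trial of 18 patients, with a mandatory pre-treatment liver biopsy supplying the tumor tissue, there are few tumor-normal pairs to spare.

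**Working it through.** The plan states no figure on this point, so there is nothing to reproduce. The check has two parts.

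**1. The passages side by side.**

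| Place | Germline sample | Fraction named |
|---|---|---|
| Section 5.3, plasma bullet | stored as companion to tumor sequencing | plasma |
| Section 5.3, cell bullet | not mentioned (immune assays only) | mononuclear cells |
| Section 12, note 19 | drawn at screening | none |
| Section 12, note 20 | not mentioned | PBMC, serum, plasma |

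One passage names a fraction for germline DNA, and it names plasma. No passage assigns a cellular fraction to that purpose. Notes 19 and 20 both apply at screening, so mononuclear cells are already isolated at that visit.

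**2. How much could be lost (illustration).** These inputs are assumptions and none is in the documents:

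- f: fraction of plasma DNA that comes from tumor, varied from 1% to 60%
- d = 100: reads covering the site in the comparator
- the variant is clonal, heterozygous and in a diploid region, so its expected allele fraction in plasma is v = f/2
- removal rule: the variant is dropped if at least k of the d reads carry it

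The number of variant reads X is Binomial(d, v), and the chance of removal is P(X ≥ k).

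Worked case, f = 10%, k = 3: v = 0.05.
- P(X=0) = 0.95^100 = 0.006
- P(X=1) = 100 × 0.05 × 0.95^99 = 0.031
- P(X=2) = 4950 × 0.05² × 0.95^98 = 0.081
- P(X ≥ 3) = 1 − 0.118 = 0.882

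The same calculation over the range of f and four rules gives:

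| f | v | ≥2 reads | ≥3 reads | ≥5 reads | plasma allele fraction ≥20% (≥20 reads) |
|---|---|---|---|---|---|
| 1% | 0.005 | 9% | 1.4% | <0.1% | 0% |
| 5% | 0.025 | 72% | 46% | 11% | 0% |
| 10% | 0.05 | 96% | 88% | 56% | 0% |
| 20% | 0.10 | >99.9% | 99.8% | 98% | 0.2% |
| 40% | 0.20 | >99.9% | >99.9% | >99.9% | 54% |
| 60% | 0.30 | >99.9% | >99.9% | >99.9% | 99% |

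Depth matters too. For f = 5% and k = 3 the removal chance is 19% at 60x, 46% at 100x and 88% at 200x.

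The loss rises with f under every rule. At f = 10% it runs from about 0% to 96% on the choice of rule alone.

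**The case against.** The strongest reply is that the documents do not settle which blood fraction the laboratory will sequence. Note 19 lists the germline draw separately from the PBMC, serum and plasma collection and leaves its fraction open. The Laboratory Manual may fix a cellular source. Cells are banked at screening and later, so a laboratory could turn to them at analysis. The work is exploratory, and whole exome sequencing is only one possible analysis.

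Most of this stands, and it limits the point. It does not remove it. Note 19 is silent on the fraction, so it neither supports nor cures the plasma wording. A manual that used cells would contradict Section 5.3, and the protocol sentence would still need correcting. Banked cells help only if some are kept from the immune assays to which they are now assigned.

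A reader might infer more than the documents support:

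- **That true mutations will be subtracted.** With tumor fraction, depth and filter rule all unstated, the loss could be negligible or nearly complete.
- **That the calendar also specifies plasma for germline DNA.** Note 19 does not mention plasma. Note 20 does, but not for germline use.
- **That mutation burden or neoantigen results will be biased in step with prognosis.** Neither is named as an output, and no biomarker test is prespecified.

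**Conclusion.** The concern holds as a minor one. The only sentence that names a fraction for the germline comparator names one that can carry tumor DNA, in a population with untreated metastatic disease at the time of the draw. This is an unsuitable specimen named in the text, not merely a detail left open.

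The size cannot be fixed from the documents. On the stated assumptions (100x, clonal heterozygous variant, removal at 3 or more reads) the loss is material from a tumor fraction of about 5%. Under a rule that requires a germline-like plasma allele fraction of at least 20%, it is negligible up to a tumor fraction of 20%.

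The effect is confined to the exploratory objective in Section 13.8. The 6-month PFS endpoint, the 6-of-16 decision rule, the sample size and the toxicity monitoring are untouched.

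**What to change.** Replace the plasma bullet in Section 5.3 with wording such as: *Germline DNA will be extracted from an aliquot of the mononuclear-cell or buffy-coat fraction of the screening blood; plasma will be kept for other uses.* Name the same fraction in note 19 of the Study Calendar and in the Laboratory Manual, and have the Manual reserve the aliquot before cells are released for immune assays.

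The cost is one sentence in the protocol and matching edits in the other two places. No extra draw should be needed, because PBMC are already isolated at screening. The downside is that a small PBMC aliquot is no longer available for the immune assays.
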